- **7.3.1 Study Drug Administration**. When a patient is diagnosed with delirium, randomization will be carried out by the investigational pharmacist at each study center according to the randomization scheme provided by the study's primary biostatistician. At each study center, the pharmacist will prepare and deliver study drug to the bedside nurse according to orders placed by study personnel. Study drugs, all clear liquids that are stable in a syringe for up to 24 hr at room temperature, will be delivered via titrated doses throughout the trial according to the administration rules in the table below:

Drug	Diluent	Equivalent Dose	Concentration
Haloperidol, USP	Provided in solution	5 mg	5 mg / mL
Ziprasidone 20 mg vial	Sterile water, 2.2 mL	10 mg	10 mg / mL
Placebo/Normal Saline, USP	Provided in solution	Placebo	Placebo

MIND-USA Protocol Version: 1.15 Confidential Protocol Date: June 22, 2016 19 of 51

- [1] **Route and Concentration**. All study drug will be administered intravenously (IV) by bolus over up to 5 minutes at concentrations of 5 mg/mL haloperidol or 10 mg/mL ziprasidone. Patients will only receive study drug while in the ICU and thus will be monitored with continuous telemetry as per usual ICU practice.
- Dosing Range. Study drug dose will be titrated in a double-blind manner according to clinical effect (see **Titration** section below). For patients in the haloperidol group, dose will range from 2.5mg (1.25 mg dose for patients  $\geq$  70 years old) to 10 mg of haloperidol IV q12 hours (maximum, 20mg/day), in keeping with numerous clinical practice guidelines. This upper limit dose for haloperidol is below the threshold for excess  $D_2$  receptor occupancy in order to avoid extrapyramidal side effects  $^{78,106,109,111,222}$  and within the pharmacokinetic range established to achieve the pro-cognitive effects of the drug. For patients in the ziprasidone group, dose will range from 5 mg (2.5 mg dose for patients  $\geq$  70 years old) to 20 mg of ziprasidone IV q12 hours (maximum, 40 mg/day) in keeping with the package insert for ziprasidone IM and recent case reports and case series of IV administration.  $^{139,142}$

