- Initiation. A pre-randomization 12-lead ECG will be obtained prior to study drug initiation to assess QTc. If this ECG shows QTc  $\geq$  550 ms, randomization and study drug initiation will be delayed until reversible causes for the QTc prolongation are found and treated. When the QTc becomes < 550 ms, randomization may occur and study drug may be started. For those patients whose ECG shows QTc < 550 ms, the first dose of study drug will be administered immediately after delirium diagnosis and randomization at a dose of 2.5 mg haloperidol IV (or 1.25 mg for patients  $\geq$  70yrs old), 5 mg ziprasidone IV (or 2.5 mg for patients  $\geq$  70yrs old), or 0.5 mL placebo (or 0.25 mL for patients  $\geq$  70yrs old).
- [4] **Titration**. After study drug initiation, subsequent study drug doses will be titrated twice daily—with all doses being delivered at approximately 10AM or 10PM—by doubling (increasing by 100%) or halving (decreasing by 50%) the volume according to the following rules. \*Note: An exception to this schedule will occur if the initiation dose is given after 4PM, in which case the second study drug dose will be given approximately 6 hours after the initiation dose (rather than at 10PM).
  - (a) Titrating Up. If study drug is not at maximum dose, the volume will be doubled approximately every 12 hours until the maximum dose is reached (10 mg haloperidol/20 mg ziprasidone/2 mL placebo q12h) unless [1] the patient cannot be assessed with the CAM-ICU due to coma (see section 7.3.1.[4].(b) below) or [2] study drug has been restarted after being held for safety reasons (see section 7.3.1.[5] on Holding study drug). If study drug has been held and then restarted (see section 7.3.1.[5] on when study drug can be restarted after Holding), the volume will not be titrated up but will instead be maintained at half the dose that had been held as long as side effects do not recur.
  - (b) Maintaining Current Dose. If a patient cannot be assessed with the CAM-ICU due to coma that is drug-induced (i.e., RASS -4 or -5 while receiving sedatives), study drug will be maintained at the current volume. Note: Sedative-induced coma is not considered a safety reason to hold study drug, whereas study drug will be held if sedatives have been held > 12 hours and the patient is comatose (per section 7.3.1.[5].(c) below).

MIND-USA Protocol Version: 1.15 Confidential Protocol Date: June 22, 2016 20 of 51

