- (c) Titrating Down. If a patient is determined to be CAM-ICU negative (i.e., not delirious) on two consecutive assessments, the study drug volume will be halved approximately every 12 hours to a minimum volume of 0.25 mL. When a patient has been CAM-ICU negative for 4 consecutive study CAM-ICU assessments, study drug will be discontinued regardless of the dose.
- (d) Restarting Study Drug. If at any time during the Treatment Period a patient is noted to develop a new episode of delirium **and** is in the ICU setting, study drug will be restarted at the dose most recently administered, as long as study drug was not discontinued permanently for safety reasons (see **Permanent Discontinuation** section below). If study drug is restarted after being temporarily held for safety reasons (as described in section 7.3.1[5]), it will be restarted at half the dose that was being administered when the safety concern was noted and prompted the study drug to be held.
- [5] **Holding**. Throughout the trial, study drug will be temporarily held for the following safety reasons:
  - (a) QTc Prolongation (≥ 550 ms). If a pre-dose 12-lead ECG (obtained per sections 7.3.1.[5].(a).(i) or (iii) below) confirms QTc ≥ 550 ms, study drug will be held. If a reversible cause for the QTc prolongation is found and treated and QTc becomes < 550 ms, study drug may be resumed at half the previous dose (not less than the minimum volume of 0.25 mL) as in our MIND pilot study and other recent studies. During the Interventional Trial Phase, QTc will be measured as follows:
    - (i) A pre-randomization 12-lead ECG will be obtained prior to study drug initiation.
    - (ii) Subsequently, QTc will be checked and documented prior to the administration of each dose of study drug, either manually calculated from a bedside telemetry strip using the Bazett formula (QTc = QT /  $\sqrt{RR}$  interval) or via software algorithms available in some bedside telemetry machines. Whenever these pre-dose measurements show a QTc  $\geq$  550 ms, a 12-lead ECG will be obtained to confirm that QTc  $\geq$  550 ms.

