  - (b) Extrapyramidal symptoms (EPS). If the patient develops clinical EPS, including dystonia and/or symptoms detected by the modified Simpson-Angus Scale(see section 7.3.2.[2]), then the study drug will be held and the patient treated as clinically indicated by the ICU team, who will be notified of the EPS by study staff. Upon resolution of EPS, study drug will be resumed at half the previous dose (not less than the minimum of 0.25mL).
  - (c) Oversedation. If the patient is oversedated (i.e., > 1 RASS level deeper than ICU team's sedation target), two sequential steps will be taken: [1] **sedatives** (including analgesics being used for sedation) will be held or decreased for > 12 hours per the ICU team's standard protocol and study drug will be maintained at current dose or titrated per standard titration rules (see section 7.3.1.[4]), then [2] **study drug** will be held if sedatives have been held > 12 hours and the patient remains oversedated. In this case, study drug will be restarted at half the previous dose (not less than the minimum of 0.25 mL) when oversedation resolves (i.e., RASS is within 1 of the ICU team's target).

MIND-USA Protocol Version: 1.15 Confidential Protocol Date: June 22, 2016 21 of 51

- [6] **Permanent Discontinuation**. Study drug will be permanently discontinued at any time during the trial for any of the following safety reasons:
  - (a) Neuroleptic malignant syndrome (NMS)
  - (b) Torsades de pointes or another ventricular tachycardia (VT) that results in clinical sequelae (e.g., hypotension) and/or requires treatment
  - (c) New-onset coma due to a known structural brain disease such as stroke, intracranial hemorrhage, cranial trauma, malignancy, anoxic brain injury, or cerebral edema
  - (d) Drug reaction with eosinophilia and systemic symptoms (DRESS) syndrome
  - (e) Any other study drug-related, life-threatening, serious adverse event

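### Protocol 7.3.1 gives two lower dose limits under age 70, applies its restart floor in some rules but not others, and leaves one oversedation case without a stated outcome

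*Protocol*

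**What the plan says.** All of this is in Protocol 7.3.1, Study Drug Administration.

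**Lower limit by age.** The Dosing Range item says of haloperidol that "dose will range from 2.5mg (1.25 mg dose for patients" aged 70 or older), and of ziprasidone that "dose will range from 5 mg (2.5 mg dose for patients" aged 70 or older). Drugs are given "at concentrations of 5 mg/mL haloperidol or 10 mg/mL ziprasidone". The Initiation item gives the matching placebo starting volume: "0.5 mL placebo (or 0.25 mL for patients" aged 70 or older).

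**Floor without age.** Item [4](c), on titrating down: "the study drug volume will be halved approximately every 12 hours to a minimum volume of 0.25 mL". Item [5] repeats the 0.25 mL floor, again without an age condition, for restart after a QTc hold (a), an extrapyramidal-symptom hold (b) and an oversedation hold (c).

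**Restart without a floor.** Items [4](a) and [4](d) also cover restart after a safety hold. Both give half the held dose, and neither states a minimum.

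**Oversedation.** Under [5](c), step 1 is that sedatives "will be held or decreased for > 12 hours per the ICU" team's usual protocol, with study drug kept at its current dose or titrated by the standard rules. Step 2 is that study drug "will be held if sedatives have been held > 12 hours and the patient remains oversedated". The note in [4](b) uses the same narrower condition for coma, and adds that coma caused by sedatives is not by itself a safety ground for holding study drug.

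**The concern.** Site staff and pharmacists act on these limits at the bedside, under blinding, in millilitres. A patient under 70 can be taken to a dose that the Dosing Range puts outside the permitted range. A patient already at 0.25 mL who is restarted after a safety hold gets a different instruction depending on which item the site reads. In the oversedation rule, step 1 opens two branches (sedatives held, sedatives reduced), and step 2 closes only one.

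At stake is uniform dosing across sites. Protocol 8.3 relies on explicit treatment protocols to make the results interpretable, and on the titration rules to limit risk. The SAP's adherence tables (doses given, held, raised or lowered, with reasons) describe what these rules produce, so a reader of those tables needs to know which rule was applied.

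**Working it through.** **1. Reproduce the plan's own volumes** (volume = dose / concentration; doses from Dosing Range, Initiation and [4](a); concentrations from Route and Concentration).
- Start under 70: 2.5/5 = 5/10 = 0.5 mL. Stated: 0.5 mL.
- Start at 70 or older: 1.25/5 = 2.5/10 = 0.25 mL. Stated: 0.25 mL.
- Maximum: 10/5 = 20/10 = 2 mL. Stated: 2 mL.

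All three agree, so the conversion is sound.

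**2. Convert the common floor back to milligrams.**
- Haloperidol: 0.25 mL × 5 mg/mL = 1.25 mg, against a stated lower limit under 70 of 2.5 mg. Ratio 2.5/1.25 = 2.
- Ziprasidone: 0.25 mL × 10 mg/mL = 2.5 mg, against 5 mg. Ratio 5/2.5 = 2.
- At 70 or older the range and the floor agree (0.25 mL, ratio 1).

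**3. Can a patient under 70 reach the floor?** I take [4](c) to mean a halving at the second and the third consecutive negative assessment and a stop at the fourth.
- From 0.5 mL: 0.25, 0.25, stop. Below the stated range at the first halving.
- From 1 mL: 0.5, 0.25, stop. Below the range at the second.
- From 2 mL: 1, 0.5, stop. A single run does not go below the range.
- One safety restart from 0.5 mL: 0.5/2 = 0.25 mL. Below the range.

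**4. Set the provisions side by side.**

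| Provision in 7.3.1 | Under 70, now at 0.5 mL | Any age, now at 0.25 mL |
|---|---|---|
| Dosing Range | no lower than 0.5 mL | under 70: already below range; 70 or older: no lower than 0.25 mL |
| [4](c) titrating down | 0.25 mL | 0.25 mL |
| [5](a)–(c) restart after hold | 0.25 mL | 0.25 mL (no reduction) |
| [4](a) and [4](d) restart after hold | 0.25 mL | 0.125 mL |

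Here 0.25/2 = 0.125 mL, which is 0.125 × 5 = 0.625 mg haloperidol or 0.125 × 10 = 1.25 mg ziprasidone.

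**5. Oversedation, by what was done with sedatives for more than 12 hours, in a patient still oversedated.**
- Held: step 1 met, step 2 met, study drug held.
- Reduced only: step 1 met, step 2 not met, and no other provision says what follows.

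**The case against.** **On the lower limit.** The Dosing Range can be read as a summary from starting dose to maximum: its lower figures equal the initiation doses, it contains no restart rule, and it refers on to the titration rules. Every operative rule takes a patient under 70 from 0.5 mL to 0.25 mL. This limits the point. A reader might infer that the restart rules disagree with one another for that patient; they do not. What stands is that the item is worded as a range for the dose, while the starting dose has its own item, so the text contains a limit that its other rules breach.

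**On the missing floor.** Items [4](a) and [4](d) refer to [5], so a reader may import the floor from there. That is reasonable, but the references concern the hold and when restart is allowed. The halving itself is written out again without the minimum.

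**On oversedation.** The narrower trigger may be deliberate. With the note in [4](b), it can be read as a design in which deep sedation is no ground for holding study drug while sedatives are still running. The note is about coma, however, and oversedation begins at more than one RASS level below target, so it does not settle the milder cases.

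**Stronger readings that the documents do not support.**
- That the two oversedation steps contradict each other, or that the hold can never operate. They leave a gap, and the ICU team can move from reducing sedatives to holding them, after which step 2 can apply.
- That raising the dose during step 1 is unaddressed. Step 1 expressly allows titration by the standard rules.
- That the gap adds noise to delirium/coma-free days. Oversedation is not the same as coma, and in sedative-induced coma [4](b) keeps the volume unchanged, so the patients whose dose could be doubled are not the ones in such a coma. Randomization is stratified by center, and the documents give no figures from which to size an effect.

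**Conclusion.** The inconsistency in lower limits holds. Under age 70 the floor in the titrating-down and restart rules is half the stated lower limit for both active drugs, and it is reached in one step from the starting volume. The restart statements also differ two-fold for a patient at 0.25 mL (0.125 against 0.25 mL), provided [4](a) and [4](d) are read as written.

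The oversedation point holds only as a mismatch between two steps that leaves the reduced-only case without a stated outcome; the narrower condition may be intended.

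The arithmetic is exact and rests only on the stated doses and concentrations. The reachability result also assumes the halving schedule in step 3 of the check. How many patients were affected cannot be derived from the documents. This is a correction to dosing text that sites act on, and it does not bear on the sample size or the planned analyses.

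**What to change.** Reconcile the items of Protocol 7.3.1:

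- State one minimum volume for each age group, and use it in the Dosing Range, in titrating down, and in every restart statement ([4](a), [4](d) and [5](a)–(c)).
- Use the same sedative condition in both oversedation steps and in the [4](b) note, or state that a reduction alone is intentionally not a reason to hold study drug.

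Which volume and which condition are right is for the sponsor's clinicians.

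The cost is protocol wording and a memo to sites. Nothing changes in sample size or data collection. The SAP already reports missing-data counts for randomized patients in the intervention period, so dosing may be complete. In that case, report which reading sites applied. The SAP's planned dose-level summaries (volume per dose, whether kept, raised or lowered, and reasons for holds) can serve for this if they are also split at age 70 and the volumes before a hold and at restart are set side by side.

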#### 7.6 Schedule of Events

		Pre- Randomization Phase	Interventional Trial Phase			
Variable* (abbreviations on next page)	Enrollment		Treatment Period	Post-Study Drug Period †	Hospital Discharge	3 & 12 Month
Demographics, Comorbidities,  Neuroimaging (CT/MRI) if		Thase	Terrou	Drug Teriou	Discharge	Nonth
available	X					
AUDIT,  ADL,  IADL/FAQ,  IQCODE,  APACHE	***					
II, 241 tobacco and illicit drug use history, employment	X					
SOFA 	X	Daily	Daily	Daily		
Pregnancy test (Beta hCG)	X					
Blood draw: APOE genotyping	X					
Urine collection: cotinine and NNAL	X					
Blood draw: CPD, IL-6, CRP, D-Dimer, sTNFr1, protein-C			Days 0,			
•			1, & 2			
Study drug levels: haloperidol & ziprasidone			Days 0,			
			1, & 2			
Hematology and Chemistry	X	Daily	Daily	Daily		
Co-administered psychoactive meds			D 1	D 1		
sedative/analgesic/antipsychotic		Daily	Daily	Daily		
RASS (target/actual),  CAM-ICU  & CPOT 		2x daily	2x daily	Daily		
BFCRS & DMSS at select participating sites		2x daily	2x daily	Daily		
Hospital-acquired infections (in blood, urine, sputum)		Daily	Daily	Daily		
ABCDE protocol compliance ‡		Daily	Daily			
12-lead ECG (baseline and subsequent ECGs)		X	See section 7.3.1.[5].(a)			
Safety assessments: Modified Simpson-Angus EPS scale, 164			7.3.1.[3].(a)			
visual analog akathisia scale, neuroleptic malignant syndrome,			Daily	Daily		
& dysrhythmia/QTc review			2 willy	2 uii		
Delirium Experience Questionnaire (DEQ) 					X	
Montreal Cognitive Assessment (MoCA) 227,228					X	
Caregiver burden interview & checklist 						X
Long-term telephone follow-up: CAM 169 neuro-						
psychological battery,  ADL,  IADL/FAQ,  EuroQOL						X
quality of life (EQ-5D), 170-172 PTSD/PCL 173, employment						
Health care costs and health status (via Medicare files)						X
Caregiver burden interview & checklist  Long-term telephone follow-up: CAM,  neuro-psychological battery,  ADL,  IADL/FAQ,  EuroQOL quality of life (EQ-5D),  PTSD/PCL  , employment	DACHE II	Acuta Physicle	gia Chronia	Health Evalve		

\*Abbreviations (alphabetical): ADL- activities of daily living, APACHE II- Acute Physiologic Chronic Health Evaluation II, APOE-apolipoprotein-E, AUDIT-Alcohol Use Disorders Identification Test, BFCRS- Bush Francis Catatonia Rating Scale, CPOT- Critical-Care Pain Observation Tool, CAM- Confusion Assessment Method, CAM-ICU- Confusion Assessment Method for ICU, CRP- C-reactive protein, DMSS- Delirium Motor Subtype Scale, ECG- electrocardiogram, EPS- extrapyramidal symptomatology, FAQ- Functional Activities Questionnaire for IADLs, IADL- instrumental activities of daily living, IL-6- interleukin 6, IQCODE- Informant Questionnaire of Cognitive Decline in Elderly, NNAL- 4-(methylnitrosamino)-1-(3-pyridyl)-1-butanol, PCL- PTSD checklist, PTSD- post traumatic stress disorder, RASS- Richmond Agitation Scale, SOFA- Sequential Organ Failure Assessment, sTNFr1- soluble TNF receptor 1 † Post-Study Drug Period\*: For patients who receive no study drug after day 10 post-randomization, daily monitoring will conclude at the end of the Treatment Period (i.e., at hospital discharge, death, or day 14 post-randomization, whichever occurs first) because the Post-Study Drug Period for these patients will be contained within the Treatment Period. Patients who continue to receive study drug after day 10 post-randomization will be monitored through the end of the Post-Study Drug Period, which will extend beyond the Treatment Period. † ABCDE Protocol: Awakening Breathing Coordination, Delirium monitoring/management, & Early mobility/Exercise; NOTE: Each component of this standardized approach to patient care, referred to as the "nonpharmacologic delirium protocol," (see section 7.2.1) will be tracked daily in all patients once consented.

Unless the participant has been discharged from the ICU; non-ICU patients will be assessed 1x daily in the Treatment Period.

MIND-USA Protocol Version: 1.15 Confidential Protocol Date: June 22, 2016 27 of 51

7.7 The Vanderbilt Coordinating Center (VCC). The VCC has extensive experience in the conduct of large, phase III clinical trials over the past decade and is comprised of over 50 people on-site at Vanderbilt. The VCC will perform (among other functions) the following: communicate with the FDA using a schedule of reporting in accordance with IND policies, design the database and data collection tool, establish a web-based data database, conduct startup meetings and site-training regarding protocol implementation and delirium monitoring to standardize all research activities during the trial, monitor enrollment pace and quality to ensure patients meet the inclusion/exclusion criteria, maintain blinding, track adverse events and ensure safety reporting, ensure protocol compliance, store plasma, serum, and genetic samples for planned and future analyses, conduct follow-up phone testing of neuropsychological function and quality of life via neuropsychology technicians, and work with the study centers and local study personnel using multiple proven patient retention techniques that have consistently achieved over 80% follow-up during previous studies.

#### 8.0 Risks

- 8.1 Side Effects of Study Drug (Haloperidol and Ziprasidone). The risks of antipsychotics (haloperidol and ziprasidone) include tardive dyskinesia, neuroleptic malignant syndrome, extrapyramidal side effects (EPS), torsades de pointes and other arrhythmias, and hyperglycemia. Throughout the Interventional Trial Phase, study personnel will carefully monitor all patients for evidence of these potential adverse effects of the study drugs. These assessments are described above in section 7.3.2. Adverse events will be monitored closely and reported as described below in Section 9.0. Should any of these occur, adverse events will be reported to the coordinating center, with Serious Adverse Events reported within 24 hours. In addition, study drug will be titrated, held, or permanently discontinued, depending on the adverse effect, according to study protocol (see section 7.3.1). Both haloperidol and ziprasidone are pregnancy category C medications, and female patients of childbearing age must have a negative pregnancy test to meet entry criteria.
- **8.2 Risks from Blood Draws.** All patients will have blood drawn for research purposes. Having blood drawn is commonly painful, and it can rarely lead to bleeding, bruising, or infection at the site of the blood draw. For this reason, it will be our standard approach whenever possible to obtain blood for research purposes through existing intravenous peripheral, central or arterial catheters since patients routinely have such catheters while in the ICU. The volume of blood collected for research specimens represents a small percentage of the amount of blood taken during the course of a standard ICU stay and will not represent a significant risk to the patient.
- **8.3 Steps Taken to Reduce Risks and Increase Impact of Study**. We have taken the following steps in designing our protocol to minimize risk for the study population and to maximize the ultimate impact of this investigation on the field of medicine.
  - [1] All interventions included in the MIND-USA study are supported by a well-grounded and clearly described rationale suggesting potential, though unproven, benefit for eligible patients.

MIND-USA Protocol Version: 1.15 Confidential Protocol Date: June 22, 2016 28 of 51

- [2] All interventions are common and with established equipoise within the context of usual care and considered good or competent care in light of an absence of clear proof in favor of one over the other.
- [3] Experts in the fields of critical care, geriatrics, psychiatry, neuropsychology, nursing, pharmacology, and clinical trial design have developed the interventions being studied.
- [4] The management of patients in all three treatment groups will be guided by explicit MIND-USA protocols so that the results of the trial can be clearly interpreted and imitated, where appropriate, in clinical practice. This will also allow for the use of the "superior group" as a control in future trials.
- [5] The MIND-USA protocol will adjust study drug dose to meet individual patient needs in the attempt to deliver safe and effective care to critically ill older and younger patients. This protocol is explicitly designed and drafted from landmark trials as referenced to meet patients' needs over time and provide individualized care.
- [6] The titration protocol for study drug and the rescue protocol for hyperactive delirium are both designed to minimize risks in comparison to anticipated benefits.
- [7] Because no placebo-controlled trials of interventions for ICU delirium exist to direct our study design, we conducted the feasibility pilot studies described in sections 3.4 and 3.5 prior to proceeding with the design of this definitive phase III trial.
- [8] An independent and qualified data safety monitoring board (DSMB) will be established (see section 9.3) to review the research protocol prior to the start of the study and conduct interim analyses for safety and review data on serious adverse events as close to real-time as possible.
- [9] We have worked very closely with the FDA to make certain that this proposal is safe and that they agree with our planned oversight and approach to due diligence in monitoring and reviewing all adverse events during the conduct of the trial. We have an active and approved **FDA-IND** #104322 for this 3-group study including both typical antipsychotic haloperidol and the atypical antipsychotic ziprasidone as well as placebo.
- [10] Rigorous monitoring and reporting of prospectively defined Adverse Events (AEs) Serious Adverse Events (SAEs), and Suspected Unexpected Serious Adverse Reactions (SUSARs) will be conducted as outlined in section 9.2 to comprehensively monitor safety during the trial.

